3.3 Virtual Facilitation Period

After the implementation outcome surveys have been completed, pharmacies will "crossover" to the virtual facilitation period(s). This period will begin with a virtual site visit from a trained virtual facilitator and be followed by at least weekly calls with a local champion (a participating pharmacist) and at least bi-weekly calls with each participating pharmacist to provide feedback on intervention fidelity (from observations of interventions delivered). The virtual site visit over Zoom will establish the personnel and workflows at each pharmacy and allow the facilitator to establish rapport. Weekly Zoom calls will allow the virtual facilitator to work with a site champion to review overall implementation challenges associated with approaching patients, delivering the intervention, and documenting results. Lastly, either the facilitator or the local champion can request and schedule a Zoom call to go over any pressing implementation issue in need of rapid attention (e.g., technical difficulties with the website).

During each 8-week virtual facilitation period (one or two periods, depending on the step to which pharmacies are randomly assigned), pharmacists will again be asked to implement the intervention with 10 vaccine hesitant patients. Like during the standard implementation period, pharmacists will use Qualtrics or a paper survey to document the extent to which the intervention results in customers getting vaccinated. Similarly, fidelity observations (4-8 total per pharmacy) will be collected using the same processes described in Section 3.2. Additionally, at the end of virtual facilitation period(s) participating pharmacy staff (up to 5 per pharmacy) will again be asked to complete Qualtrics surveys to assess implementation outcomes (feasibility, acceptability, appropriateness).

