To increase the likelihood that each participating pharmacy submits the requested study data, a fax will be sent to each participating pharmacy that is missing data after the first month of standard implementation to remind them of what is needed. This fax may be sent every 2 weeks as needed to acquire missing study data, with a follow-up phone call a week after the fax to non-responders.

At the end of the standard implementation period(s), participating pharmacy staff (up to 5 per pharmacy) will complete Qualtrics surveys to assess implementation outcomes (feasibility, acceptability, appropriateness).

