4.2 Secondary Outcome

The secondary outcome of effectiveness will be assessed on a monthly basis. Pharmacists will be instructed to deliver vaccine hesitancy counseling to one to two vaccine-hesitant individuals each week (towards a target of at least 5 per month). Using Qualtrics or a paper survey, pharmacists will document the following on a daily basis: A) how many vaccine-hesitant individuals they provided vaccine hesitancy counseling to; B) of those individuals, how many received a COVID-19 vaccine; C) the self-reported age, race, and gender of the individual who was counseled.

Effectiveness will be calculated as the proportion of counseled individuals who received a vaccine, or B/A. Individuals who are counseled and schedule a vaccine at a later date will not be counted in the numerator (B) until they have actually received a vaccine. Effectiveness scores will range from 0 to 1, with higher scores reflecting a greater percentage of vaccine-hesitant individuals who received a vaccine. During virtual facilitation, trial facilitators will be provided with bi-weekly effectiveness data so they can share the results with the pharmacies to assess performance and identify ways to improve implementation processes and intervention effectiveness.

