4.3 Other Measures

Acceptability, appropriateness, and feasibility of the vaccine hesitancy intervention and implementation approaches (standard, facilitation) will be measured using validated surveys³³. Each

measure includes 4 items (e.g., “intervention X seems doable” [feasibility]) measured on a 5-point response scale that ranges from “strongly disagree” (coded as 1) to “strongly agree” (coded as 5). For each pharmacy, we will average scores across the pharmacy staff members who complete the surveys.

Uptake will be calculated as the number of times vaccine hesitancy counseling was offered divided by the number of individuals who expressed vaccine hesitancy when offered the vaccine.

Sustainment will be assessed by the continued measurement of fidelity, effectiveness, and uptake during the “follow-up” periods.

*Organizational structure and context measures*³⁴: one pharmacist per pharmacy will complete the Organizational Structure survey^{35,36}, which measures: location, type (e.g., independent, chain), setting (e.g., retail, specialty), size (weekly prescriptions, staffing), technological capacity (dispensing system), and services provided. The Organizational Context measure (completed by 5 pharmacy staff members) assesses CFIR inner setting constructs³⁴ that reflect organizational culture/capacity for change³⁷, learning climate, leadership, and resources^{38,39}. All items are measured on a 5-point agree-disagree response scale, with higher scores reflecting a stronger implementation context. For each pharmacy, we will average scores across the five pharmacy staff members who complete the surveys.

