5.3 Power Analyses

For the primary outcome of fidelity, captured at the pharmacy level, we wish to compare the fidelity scores under standard implementation versus fidelity scores under virtual facilitation. We expect each pharmacy to have approximately 4 fidelity assessments per time period (i.e., a period of 8 weeks). A sample of 30 pharmacies in an incomplete stepped-wedge cluster-randomized design with six periods (five steps), and an average of 10 fidelity assessments per pharmacy yields a total sample size of 320 assessments, which achieves over 90% power to detect a difference between means of 0.53 with a standard deviation of 1 (i.e., moderate effect size). The test statistic is based on a two-sided Wald Z-test with $ICC = 0.6$ and $\alpha = 0.05$. Given that we will have repeated fidelity measures from the same pharmacists over time, we have specified a conservative ICC (which in a stepped wedge design does not impact power calculations significantly).

For the secondary outcome of effectiveness, we expect each pharmacy to identify approximately 10 vaccine-hesitant patients during each time period (i.e., a period of 8 weeks). A sample of 30 pharmacies in an incomplete stepped-wedge cluster-randomized design with six periods (five steps) and an average of 27 patients per pharmacy yields a total sample size of 800 patients, which achieves over 90% power to detect a difference between effectiveness proportions of 10%. The proportion of vaccine-hesitant patients accepting the vaccine during the virtual facilitation approach is assumed to be 15% compared to 5% under the standard implementation period. These estimates are based on a review of reported changes in vaccine acceptance for evidence-based vaccine hesitancy interventions⁴⁰. The test statistic is based on a two-sided Wald Z-test with $ICC = 0.05$ and $\alpha = 0.05$. We note that the actual sample size should exceed 800 patients since we expect pharmacies will continue to identify vaccine-hesitant individuals during the follow-up periods.

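### Effectiveness (B/A) is computed on patients chosen by pharmacists who know the condition, with no common entry rule and no record of initial hesitancy, so case mix and outcome capture can shift at crossover in either direction

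*Combined protocol and SAP*

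**What the plan says.** Section 4.2 defines effectiveness as B/A, where A counts only people who were counselled. On who enters A it says "Pharmacists will be instructed to deliver vaccine hesitancy counseling to one to two vaccine-hesitant individuals each week". Section 6.1 likewise leaves it to the pharmacist to identify them. Neither section gives a rule for choosing among hesitant customers or asks how hesitant the person was beforehand. Blinding is stated only for the fidelity raters (Section 4.1).

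The support around the pharmacist differs by condition:

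- **Facilitation.** Weekly calls with the site champion serve to "review overall implementation challenges associated with approaching patients, delivering the intervention, and documenting results" (Section 3.3). Section 4.2 adds that "trial facilitators will be provided with bi-weekly effectiveness data so they can share the results with the pharmacies", with the aim of improving effectiveness.
- **Standard.** The webinar covers documentation (Section 6.2). For missing submissions, "a fax will be sent to each participating pharmacy that is missing data after the first month of standard implementation", repeated every two weeks as needed, with a phone call to non-responders a week later (Section 3.2).

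Section 5.2 recognises a possible bias. Its remedy is to have pharmacists approach, during facilitation, people they had not approached before. Step 3 of the model adjusts for age, race, gender and pharmacy-level factors such as size. Uptake (Section 4.3) has a wider denominator, "the number of individuals who expressed vaccine hesitancy when offered the vaccine", but is a separate measure that does not enter the effectiveness model.

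**The concern.** Randomizing pharmacies to blocks makes the pharmacies comparable. It does not make the patients comparable when staff who know the condition choose them after crossover. If the people logged under facilitation are more, or less, open to vaccination than those logged under standard implementation, B/A changes even though counselling works no better. The same applies if refusals or later vaccinations are recorded more completely in one condition.

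At stake is the reading of H2. An odds ratio above 1 could reflect better counselling, an easier case mix or different logging. An odds ratio near 1 could hide a real benefit if facilitation brought in firmer refusers or better recording of refusals.

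**Working it through.** **1. The plan's own figures.** Section 5.3 states that "an average of 27 patients per pharmacy yields a total sample size of 800 patients, which achieves over 90% power". The facilitation rate "is assumed to be 15% compared to 5% under the standard implementation period", with ICC 0.05 and a two-sided Wald test at 0.05.

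- Pharmacy-periods in Figure 1, without follow-up: 5 × (2+3+3+2+3+3) = 80, of which 40 are standard and 40 facilitation. At 10 patients each, 80 × 10 = 800, and 800/30 = 26.7 per pharmacy. The sample size reproduces.
- Power = Φ(|difference|/SE − 1.96), with SE from a linear mixed model on the Figure 1 layout (random pharmacy effect). With period effects and the variance at 5%, SE = 0.0294 and power is 92.5%. With period effects and the mean variance of the two conditions, SE = 0.0399 and power is 70.7%. Without period effects and with the mean variance, SE = 0.0209 and power is 99.8%. Over 90% is thus reproducible under some choices. That sensitivity is a separate matter.
- The planned effect in counts: 400 × 0.05 = 20 against 400 × 0.15 = 60. The 40 extra vaccinations over 40 facilitation pharmacy-periods are one per pharmacy per 8 weeks.

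**2. What could hold case mix constant at crossover.**

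| Feature | What it controls | What it leaves open |
|---|---|---|
| Block randomization (2.2) | Differences between pharmacies | Which patients are chosen after crossover |
| Period adjustment (5.2, step 2) | Calendar time | A shift that occurs with the condition |
| New-patients instruction (5.2) | Counting the same person in both conditions | Comparability of the two pools; the second is what the first left |
| Age, race, gender, size (5.2, step 3) | Those factors | Initial hesitancy |
| Uptake (4.3) | Shows the share of hesitant people offered counselling | Strength of hesitancy; not linked to the model |

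The boundary of A is also loose. Section 3.2 records customers offered the intervention, and Section 4.2 records those counselled. Table 2 lets people who are not ready go straight to the last step, without saying whether they count in A.

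**3. Illustration of a case-mix shift.** The documents give no acceptance rates by degree of hesitancy, so these are assumptions. Let firm refusers accept at p_f and unsure people at p_u, with no facilitation effect on anyone. Then rate = p_f + share × (p_u − p_f), so share = (rate − p_f)/(p_u − p_f). The odds ratio is taken against 5%.

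| Rate observed | Odds ratio | Unsure share, 2%/20% | Unsure share, 3%/25% | Unsure share, 0%/50% |
|---|---|---|---|---|
| 5% | 1 | 0.03/0.18 = 17% | 0.02/0.22 = 9% | 10% |
| 7.5% | 1.54 | 0.055/0.18 = 31% | 20% | 15% |
| 10% | 2.11 | 0.08/0.18 = 44% | 32% | 20% |
| 15% | 3.35 | 0.13/0.18 = 72% | 55% | 30% |

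In the other direction, with 2%/20%, a fall in the share from 17% to 10% gives 0.02 + 0.18 × 0.10 = 3.8%, and an odds ratio of (0.038/0.962)/(0.05/0.95) = 0.75.

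**4. Illustration of a capture shift.** Suppose the true rate is 5% throughout, but half of the standard-condition denominator goes unlogged, all of it refusals. Standard then reads 20/200 = 10% against a fully logged 20/400 = 5% under facilitation. The odds ratio is (0.05/0.95)/(0.10/0.90) = 0.47. Swapping the conditions gives 2.11.

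**5. Chance of a significant result from selection alone.** With the mean variance, a shift from 5% to 10% has SE = 0.0354 with period effects, giving 29%. Without period effects (as in step 1 of the model) the chance is 77%. The nominal level is 5%.

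**6. Would the proposed covariate help?** In the model of item 3 the odds ratio within each class is 1 by construction. Adjusting for an accurate no/unsure field would therefore remove the distortion. To the extent that the field is misrecorded, distortion remains.

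**The case against.** The strongest reply is that monitoring, feedback and problem-solving are the strategy under test (Section 6.3). In an implementation trial, a change in how patients are approached may belong to the facilitation effect. This stands in part: the facilitator calls should not be altered. But reaching more hesitant people would show in uptake, and the trial still needs to tell that apart from logging more persuadable people.

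Four stronger readings are tempting, and the documents support none of them.

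- *Facilitation tells pharmacists whom to pick.* Section 3.3 speaks of reviewing challenges in approaching patients and says nothing about choosing among them.
- *The standard condition has only a fax.* It also has the follow-up phone call (Section 3.2) and training in documentation (Section 6.2). Nor does the text say that reminders stop at crossover. The difference is one of intensity.
- *The bias favours facilitation.* Feedback on B/A could encourage easier choices. Better logging of refusals, or a leftover pool of harder patients under the new-patients instruction, would push the other way.
- *Selection could readily produce the whole planned effect.* With 2%/20% that needs the unsure share to go from 17% to 72%. Nothing in the documents suggests a shift of that size.

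It is also fair to say that uptake and effectiveness come from the same monthly report (Table 1), so some changes would be visible by condition. Because uptake does not measure strength of hesitancy, this is only a partial safeguard.

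**Conclusion.** The concern holds as a risk of bias of unknown size and direction, confined to the secondary outcome. It rests on three facts in the text: the pharmacist chooses who enters A, no common rule or initial-hesitancy record is stated, and support for approaching patients and documenting results intensifies at crossover. That pharmacists know the condition follows from the start of the calls.

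The odds ratios above (0.47 to 3.35) rest wholly on assumed acceptance or logging rates. They show that the outcome is sensitive to selection and capture, not that bias will occur. A reader might infer that the primary result is also in doubt. It is not: fidelity is rated by blinded staff in scheduled sessions with standardized patients and randomized scripts (Sections 3.2 and 4.1).

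The plan should be changed because the remedy is cheap and, without it, the odds ratio cannot be attributed to better counselling.

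**What to change.** - **Section 4.2:** define A identically in both conditions as the first one to two people each week who answer no or unsure at the ASORT Ask step, entered in the log before counselling starts. Keep the existing target of about 10 per 8-week period; a fixed two per week would give 2 × 8 = 16. Pharmacists may still counsel anyone.
- **Log and Section 5.2:** add a no/unsure field and include it in step 3. Section 8.2 says effectiveness data are recorded in aggregate. That should be reconciled with step 3, which already needs patient-level age, race and gender.
- **Reporting:** show uptake and the no/unsure mix by condition beside the odds ratio.
- **Sections 3.2 and 3.3:** state that the same missing-data reminders go out on the same schedule in both conditions. Leave the content of the facilitator calls unchanged.

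The cost is one tick-box, one instruction, one covariate and a few seconds per entry, made in real time, with less freedom over who is logged. The change reduces the bias but does not remove it, because unblinded pharmacists still choose whom to ask and complete the field themselves.

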3.4 Follow-up

Pharmacies randomized to blocks 1-4 will have one 8-week follow-up period. During this period, pharmacists will continue to use Qualtrics or a paper survey to document the extent to which the intervention results in customers getting vaccinated. They will specifically document the number of customers they offered the intervention to, the number who refused, and the number who agreed to be vaccinated.

3.5 Qualitative Data Collection

After pharmacies complete both the standard and virtual facilitation periods, study staff will conduct qualitative interviews with the primary study participant from one high performing and one low performing pharmacy in each block (12 pharmacies total) to assess feasibility and performance of the implementation approaches. It will also assess: 1) associations observed for organizational structure and culture/climate measures associated with fidelity and effectiveness, 2) sustainability potential, and 3) costs at the pharmacy level. Each interview is expected to last 60 minutes.

4 STUDY EVALUATIONS AND MEASUREMENTS

4.1 Primary Outcome

Our primary outcome is fidelity to the vaccine hesitancy counseling intervention, assessed at the pharmacy level. Our fidelity measure is based on a theoretical framework of fidelity measurement³⁰ as well as a validated fidelity checklist³¹. The fidelity measure focuses on the competence of the pharmacist (7 items) in their delivery of the vaccine hesitancy counseling intervention.

The competence items focus on the skillfulness of intervention delivery: expressed empathy; used a non-confrontational manner; spoke confidently without using jargon; emphasized patient autonomy; reflected back patient's statements accurately; used a respectful demeanor, and used evidence-based responses when responding to patient vaccine concerns. Each competence item will be assessed on a scale from 0 to 2, with 0 = skill not demonstrated, 1 = skill needs development, and 2 = skill demonstrated with competence. Competence scale scores will range from 0 to 14, with higher scores reflecting greater competency in the delivery of ASORT. Fidelity will be measured for each pharmacist approximately twice per month under the standard implementation approach and approximately twice per month under the virtual facilitation approach. In pharmacies with more than one pharmacist, fidelity ratings will be averaged to achieve a pharmacy-level measure.

Trained staff will rate fidelity after reaching 80% inter-rater reliability during training³². Staff who are blinded to the pharmacist's group assignment will use a fidelity observation guide to rate pharmacists' vaccine hesitancy counseling during recorded counseling sessions. During virtual facilitation, ratings will be shared with the facilitators who provide feedback and coaching to pharmacists towards improving fidelity.

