2.3 Number of Subjects and Study Duration

The stepped-wedge trial includes 30 pharmacies and up to 150 subjects. Subjects will include 30 pharmacists (1 from each pharmacy) and up to 120 pharmacy staff (up to 4 staff from each pharmacy), such as pharmacy technicians and cashiers. Pharmacies will participate in the study for 6-12 months, depending on the block to which they are randomly assigned. Total anticipated study duration will be 2 years, with 15 pharmacies participating in year 1 and 15 participating in year 2. The study follows the distribution of COVID-19 vaccines in the USA, which follows the Northern Hemisphere’s “flu season”—approximately August–February each year. We expect that the first COVID-19 vaccination season in the fall of 2023 will be delayed due to vaccine availability and will begin in October and run through March 2024. In 2024, we expect that availability issues will not occur and the vaccine will be available during the standard flu season from August–February. All pharmacies begin the study in the fall. Block 1 and blocks 4–6 will participate for 6 months (Oct–Mar and Aug–Jan, respectively). Blocks 2 and 3 begin in Oct 2023 and participate for 6 months alongside Block 1, but then have an 8-week follow-up period Aug–Sep 2024 (Figure 1).

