3.2 Standard Implementation Period

After pharmacy participants are enrolled, they will then complete one or two 8-week "standard implementation" period(s), depending on the step to which they are randomly assigned. At the beginning of this period, they will be asked to complete a 30-minute online training about COVID-19 vaccine hesitancy counseling and watch a live or pre-recorded webinar (their choice) that provides up-to-date information about COVID-19 vaccinations and boosters. After completion of the training and webinar, participants will be asked to implement the vaccine hesitancy counseling intervention with 10 vaccine hesitant patients per 8-week period. Pharmacists will use Qualtrics or a paper survey to document the extent to which the intervention results in customers getting vaccinated. They will specifically document the number of customers they offered the intervention to, the number who refused, and the number who agreed to be vaccinated. No identifiable customer-level data will be provided by the pharmacies.

Additionally, during the standard implementation period(s), trained study staff will observe and rate counseling fidelity two times per month for each participating pharmacy. We will use a fidelity rating scale to assess fidelity of delivery of the intervention during 4-8 total observed intervention sessions per pharmacy (4 per 8-week period). Since pharmacists have reported difficulties getting patients to agree to be recorded, affecting data collection, we will use standardized patients (SPs) in lieu of real patient conversations. Two SPs will have a total of 8 standardized scripts, each expressing different concerns about the Covid vaccine. The project manager will schedule a 20-minute block with an SP and participating pharmacist and send a Zoom link. Pharmacists will be randomized to script and order of the presentation of two SP scenarios. On the Zoom call, SPs will enact two of their cases, to which the pharmacist will ideally respond with the ASORT intervention. The encounter will be recorded using the secure Express Dictate mobile or desktop app and later rated for counseling fidelity. SPs will meet with each pharmacist one time per month, portraying different personas each time.

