7.3 Risks associated with fidelity observations

The risks for participating in the fidelity observations are minimal for pharmacists. Observation guide information will not be shared outside the study team, and therefore, do not pose employment risks for the pharmacist. Pharmacists will receive a study information sheet so they can make an informed decision about whether to participate. Since standardized patients will be used, there is no risk to customers of the pharmacies. The recording is made within the secure Express Dictate mobile app and encrypted recordings are only sent to study personnel, who need the encryption key and Express Dictate desktop software to open. Once the virtual coach has completed the observation guide, the recording will be permanently deleted.

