8.2 Confidentiality of the data

A secure, online survey data collection (Qualtrics) will be used to collect participant survey data. For interviews, participants will be informed that they have the right to refuse audio recording; in such cases the interviewer will take notes. For recorded interviews, the interviewer (who will be UAMS affiliated) will upload each digital recording to a password-protected file on a secure server at UAMS. Audio files will be transcribed by a professional transcriptionist who is employed by UAMS. Audio files will be maintained on the secure UAMS Server until transcription is complete and transcripts are checked for accuracy, at which time they will be destroyed. Recordings for fidelity observations will be made using the secure mobile app Express Dictate, will be encrypted, and will be maintained in secure, password-protected software or on the UNC server until observation guides are completed; then, the recordings will be permanently deleted. Completed survey data will be maintained in the secure Qualtrics system at UNC. Transcripts will be analyzed with a qualitative software package, and the findings generated with this program will be kept in the study folder on the secure server. To further protect confidentiality, we will request that no participant be referred to by name or in any way that would allow a person to be identified during the interview. Should this occur inadvertently, the name would be redacted from the transcript.

De-identified data on rates of delivering vaccine hesitancy counseling and the number of hesitant individuals who received a vaccine will be sent to and used by the study team for analysis. All pharmacy participants are trained in HIPAA compliance by nature of their employment and will not introduce additional risk beyond the normal risk associated with clinician handling of personal health information. Data from pharmacies utilized to calculate quantitative implementation outcomes and effectiveness will be stored in secure, password protected file on a UNC Server. All data on fidelity and effectiveness will

be recorded in aggregate and no identifying or personal health information of customers will be collected.

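### The rater blind on the primary fidelity score is stated but not protected, and Sections 4.1 and 7.3 conflict on who completes the rating

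*Combined protocol and SAP*

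**What the plan says.** - **Who rates.** Section 4.1: "Staff who are blinded to the pharmacist's group assignment will use a fidelity observation guide". Section 7.3, on the same recordings: "Once the virtual coach has completed the observation guide, the recording will be permanently deleted".
- **What the rating is for.** The score is the primary outcome. Section 4.1 also gives it a second use: "During virtual facilitation, ratings will be shared with the facilitators who provide feedback and coaching to pharmacists towards improving fidelity". No such release is described for standard implementation.
- **When.** Section 3.3 calls for "at least bi-weekly calls with each participating pharmacist to provide feedback on intervention fidelity (from observations of interventions delivered"). Section 3.2 says of timing only: "The encounter will be recorded using the secure Express Dictate mobile or desktop app and later rated for counseling fidelity".
- **What happens to the recording.** Section 8.2 keeps it "until observation guides are completed; then, the recordings will be permanently deleted".
- **What is scored.** Seven skill items, each 0 to 2, total 0 to 14 (Section 4.1). They include empathy, respectful demeanor and a non-confrontational manner.
- **What is not said.** The document does not mention hiding date or pharmacy from raters, shuffling the rating order, routing ratings through a third party, or keeping raters and coaches apart.

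**The concern.** Pharmacists and facilitators cannot be blinded here, so the blinded rater is the main guard against expectation in the primary outcome. The items are matters of judgement, and the study's hypothesis is that scores rise after crossover. If the coach completes the guide, the person scoring knows the condition and has an interest in the result. If separate staff score, the plan still gives them one score with two uses, one of which exists in facilitation only, and no procedure that keeps this from them.

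Deletion makes the problem permanent. If the blind is questioned when the results are read, nothing is left to re-rate.

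**Working it through.** **1. The plan's own figure.** Inputs: Figure 1 (8 standard and 8 facilitation block-periods), 5 pharmacies per block (Section 2.2), about 4 ratings per pharmacy-period (Section 5.3).

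16 × 5 × 4 = 320 ratings, as stated.

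Power: pharmacy random intercept, six categorical period effects, total variance 1, ICC 0.6, follow-up left out. The covariance of a pharmacy's period means is 0.6 between periods, plus 0.4/4 = 0.1 on the diagonal. Generalised least squares gives SE = 0.152. Power = Φ(0.53/0.1522 − 1.96) = Φ(1.52) = 93.6%, against a stated figure of over 90%. The plan's figure is reproduced.

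**2. What the calendar reveals.** Standard and facilitation ratings by period:

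| Period | Standard | Facilitation | Pharmacies in follow-up |
|---|---|---|---|
| Oct–Nov 2023 | 60 | 0 | 0 |
| Dec–Jan 2023/24 | 20 | 40 | 0 |
| Feb–Mar 2024 | 0 | 40 | 5 |
| Aug–Sep 2024 | 60 | 0 | 10 |
| Oct–Nov 2024 | 20 | 40 | 0 |
| Dec–Jan 2024/25 | 0 | 40 | 5 |

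Ratings in periods with only one of the two conditions: 60 + 40 + 60 + 40 = 200 of 320 (62.5%). Guessing the majority condition by date is right for 200 + 40 + 40 = 280 of 320 (87.5%). Section 4.3 says fidelity is also measured in follow-up, while Section 3.4 lists only the vaccination survey. If follow-up sessions are rated, only Oct–Nov 2023 is strictly single-condition (1 of 6).

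**3. How a lean reaches the estimate.** Let raters score d SD higher when they believe a session is facilitation. The documents give no value for d; 0.1 to 0.3 is an assumption. The same design matrix carries d into the estimate. The false-positive rate is Φ(−1.96 + b·d/SE) + Φ(−1.96 − b·d/SE), where b is the share of d that reaches the estimate.

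| Source of the lean | Model | b | SE | d = 0.1 | d = 0.2 | d = 0.3 |
|---|---|---|---|---|---|---|
| Condition known | Step 1, no period term | 1.00 | 0.074 | 27% | 78% | 98% |
| Condition known | Step 2, categorical periods | 1.00 | 0.152 | 10% | 26% | 50% |
| Date only (majority guess) | Step 1 | 0.81 | 0.074 | 20% | 60% | 91% |
| Date only (majority guess) | Step 2 | 0 | 0.152 | 5% | 5% | 5% |

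A date-only lean is the same for every session in a period, so categorical period effects remove it exactly.

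A lean confined to the 80 facilitation ratings in the two mixed periods still gives b = 1 in step 2. It equals d × (facilitation indicator) minus d × (indicators of the two all-facilitation periods), and the second part lies in the period effects.

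**4. Scale in points.** If the SD of the total score is 2 to 3 points (assumption), the target is 0.53 × 2 = 1.1 to 0.53 × 3 = 1.6 points. One item scored one level higher in half of facilitation sessions adds 0.5 point. That is 0.5/3 = 0.17 to 0.5/2 = 0.25 SD, or 31% to 47% of the target.

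**The case against.** The strongest reply is that 4.1 states the blind, and that sharing happens after scoring. Section 8 has study staff enter guide data into a database, so ratings could be released from there without the rater learning which ones are used. Three stronger readings are therefore tempting, and the documents do not support them.

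- **The blind cannot hold.** A reader might infer this from the routing. But nothing says that the rater sends the ratings or learns where they go. What can be said is that no protection is described.
- **Ratings must be made promptly, and turnaround betrays the condition.** Bi-weekly feedback suggests timely rating in facilitation, but no deadline is given, and nothing says standard sessions are rated more slowly. A mention of the facilitator on the call is possible, not documented.
- **The calendar unblinds four of six periods and so biases the result.** The count needs follow-up sessions to be unrated, which Section 4.3 contradicts. Even where it holds, a date-only lean leaves the period-adjusted estimate untouched. It matters for step 1 of Section 5.1, which stays relevant because none of the four steps is named as the primary estimate.

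The reply also does not meet Section 7.3. A coach who completes the guide is not blinded, and that sentence cannot stand beside 4.1 for the same score. The deletion rule stands in both sections.

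**Conclusion.** The concern holds in this form: the blind on a judgement-based primary score is asserted in 4.1, contradicted in 7.3, supported by no procedure, and impossible to repair after deletion.

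The size is conditional. If raters know the condition, the whole lean enters both the unadjusted and the period-adjusted estimate. At 0.1 to 0.3 SD, the period-adjusted test would reject a true null about 10% to 50% of the time instead of 5%. This rests on an assumed lean, the plan's ICC of 0.6, 4 ratings per pharmacy-period and categorical periods. The documents do not show that any lean will occur. The case for change is that the safeguard is cheap and the loss irreversible.

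**What to change.** 1. Reconcile 4.1 and 7.3 by defining two scores. The coach may complete a guide during facilitation for feedback; that score is not the outcome.
2. Have the existing trained raters, none of whom coaches, assign the outcome score after each season. They work from recordings labelled only with a random code and shuffled across pharmacies, conditions and months.
3. Amend 7.3, 8.2 and the information sheet so that encrypted recordings are kept until that season's outcome ratings are locked.
4. Keep the standardized patients unaware of condition, and ask pharmacists not to mention facilitation on the call.
5. Have raters record a guess of condition for each session, and report its accuracy.

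**Cost.** Recordings are held about 6 months longer, roughly one season; they contain the pharmacist and standardized patient, not customers. Coaches score 8 × 5 × 4 = 160 scenarios of at most 10 minutes (two per 20-minute block, Section 3.2): 160 × 10 / 60 = 26.7, about 27 hours in total. No new staff are needed. There is one real trade-off: coaching feedback would come from the coach's own guide and no longer from the shared blinded rating, which alters a component of the facilitation approach and should be stated.
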